3.6 Study Evaluations

3.6.1 Efficacy Evaluations

After randomization and vaccination on Study Day 0, the participants will be questioned about TB signs and symptoms at every study visit and contact, and will be instructed to come to the study site if TB signs or symptoms occur between study visits or contacts.

When there is clinical suspicion of TB disease, 2 separate sputum samples for *Mtb* testing will be obtained. 1 sputum sample will be tested by Xpert MTB/RIF Ultra. The same sputum sample will be sent for culture together with the second sputum sample for verification. The remainder of the 2 separate sputum samples is stored (frozen) as 2 separate samples for later analysis by WGS if recurrent TB is verified.

Referral for diagnosis and management of recurrent TB is triggered by the investigator based on clinical suspicion of recurrent TB. Participants will not be withdrawn from the study based on this referral but will be withdrawn if *Mtb* positive by culture in the study or if the referral clinic diagnoses recurrent TB and starts TB treatment.

In cases where the *Mtb* culture result in the study was negative or is pending, but the referral clinic diagnosed recurrent TB and started TB treatment, 2 additional sputum samples should be collected as soon as possible for repeat *Mtb* testing by culture, and the participant is withdrawn from the study.

If *Mtb* negative by Xpert MTB/RIF Ultra and subsequent verification by culture, the participant continues in the study. For further details on the case verification procedure for recurrent TB disease, see Section 2.2.

At the final study visit (V8=Day 421) or at the ET Visit, if discontinuation is not due to verified recurrent TB, 2 separate sputum samples for *Mtb* testing will be obtained from all participants (capable of producing sputum), even if there is no clinical suspicion of TB disease, in order to ensure that no cases of recurrent TB disease are missed during the study and to detect subclinical cases in this population at high risk for recurrence of TB disease. If there is clinical suspicion of TB at V8, all V8 activities will be conducted and not a STB visit since at V8 two separate sputum samples for *Mtb* testing will be obtained from all participants even if there is no clinical suspicion of TB. This is to ensure that no cases of recurrent TB disease are missed during the trial. One sputum sample will be tested by Xpert MTB/RIF ultra. If *Mtb* negative by Xpert MTB/RIF ultra but there are clinical TB signs or symptoms, verification by culture testing will be requested from the laboratory and both of the sputum samples will then be processed for culture. In this instance HIV testing and immunology sample collection should also be performed at V8.

Participants will be contacted to be given their Xpert MTB/RIF Ultra and culture result once available (whether positive or negative) and symptomatic participants will be referred as appropriate for management irrespective of the Xpert MTB/RIF Ultra and culture result. Asymptomatic participants not capable of producing sputum will be considered negative for TB disease recurrence.

Confirmation of *Mtb* by one positive sputum culture result is required for a participant to meet the primary efficacy endpoint of TB disease recurrence. For the secondary efficacy endpoints of TB disease relapse and TB disease reinfection, WGS will be performed on *Mtb* isolates to distinguish relapse from reinfection. Participants with a combined V1 and V2 will not provide sputum samples prior to starting TB treatment because their 1st screening visit (V1) would be performed on the same day as V2. For these participants, it will therefore not be possible to determine if their TB recurrence was due to relapse or reinfection.

For the exploratory efficacy endpoints, participants who started TB treatment without confirmation of *Mtb* by culture or participants with TB disease recurrence between 30 days after the 1st vaccination and 14 days after the 2nd vaccination will also be included. All efficacy endpoint definitions are given in Section 2.1.

The HIV status (i.e., to assess if seroconversion occurred since HIV test at V2) will be determined at time of diagnosis of TB disease recurrence, and the CD4 count will be determined if the participant is HIV positive.

A participant is considered to have clinical suspicion of TB when he/she presents with one or more of the following TB signs and symptoms: unexplained cough for longer than 2 weeks duration, fever, night sweats, loss of weight, hemoptysis, or other TB signs or symptoms.

3.6.2 Immunogenicity and Immunology Laboratory Evaluations

A summary of immunogenicity and immunology assays to be performed on blood specimens is shown in Table 3-2.

For the immunogenicity cohort at the [REDACTED] sites only (= first 50 randomized participants at [REDACTED] and first 50 randomized participants at [REDACTED] = in total

100 participants), see Table 2-1, whole blood will be collected for WB ICS. For the remaining participants and sites, there will be no collection of whole blood for WB ICS.

For all participants in the study, the immunogenicity / immunology samples, assays, endpoints, blood volumes, study days of collecting samples and names of laboratories analyzing the samples are shown below in Table 3-2.

Staff at the clinical study site will refer to the most current version of the Laboratory Manual (provided under separate cover) for further instructions and additional information on specimen including sputum collection and processing.

Table 3-2 Summary of Immunogenicity and Immunology Laboratory Evaluations

Sample Type	Assay	Immunogenicity/ Immunology Endpoint	Approximate Blood Volume (per Visit)	Study Days	Name and Location of Analysis Laboratory
Whole blood	WB ICS	Secondary endpoint ¹ (Primary immunogenicity endpoint)	6 mL	0 ¹ , 70 ¹	██████████
Plasma (obtained from PBMC)	IgG ELISA	Secondary endpoint ¹	Plasma (3 mL) obtained from PBMC	0 ¹ , 70 ¹	██████████
Plasma (obtained from PBMC)	IgG ELISA	Exploratory endpoint ²	Plasma (3 mL) obtained from PBMC	0 ² , 70 ² , 421 ⁵ , STB ³ , ET ⁴	██████████
Whole blood	RNA analysis	Exploratory endpoint ²	2.5 mL	0 ² , 421 ^{1,5} , STB ³ , ET ⁴	██████████
Whole blood (DLC iCE)	Blood subset count (support of RNA analysis)	Exploratory endpoint ²	At least 0.5 mL collected in a 2.0 mL tube	0 ² , 421 ^{1,5} , STB ³ , ET ⁴	██████████
PBMC	ICS	Exploratory endpoint ²	50 mL	0 ² , 70 ² , 421 ^{1,5} , STB ³ , ET ⁴	██████████

- 1) Participants in immunogenicity cohort (1st 50 randomized at ██████████ and 1st 50 randomized at ██████████)
- 2) All participants in study
- 3) Participants if STB Visit is conducted
- 4) Participants who have not already had this at a STB Visit which resulted in verification of recurrent TB and who are Xpert Ultra MTB/RIF positive at the ET Visit
- 5) Participants who are Xpert Ultra MTB/RIF positive at Visit 8 (Day 421)

For further details on the purpose of the assays and the immunogenicity/immunology endpoints, see Section 7.4.

3.6.3 Safety Evaluations

3.6.3.1 Pre-vaccination and Post-Vaccination Monitoring of Participants

Participants will have vital signs taken prior to each study vaccination. Participants will remain in the clinic under close observation for at least 60 minutes after receiving the investigational product. Vital signs will be repeated at 60±10 minutes post-vaccination before participants leave the clinic. The injection sites will be examined.

Allergic reactions to vaccination are possible, therefore, appropriate drugs and medical equipment to treat acute anaphylactic reactions must be immediately available and an investigator trained to recognize and treat anaphylaxis must be present in the clinic during the entire vaccination procedure and post-vaccination monitoring period.

3.6.3.2 Clinical Assessments and Laboratory Tests

Clinical assessments and laboratory tests to be performed at each visit are summarized in Table 3.1. Results from clinical assessments and laboratory tests obtained in the study must be reviewed by the investigator, and managed in accordance with the study site policies. The clinical significance of any change in a vital sign or laboratory parameter will be determined by the investigator, and may be reported as an AE at the discretion of the investigator. Additional laboratory tests may be performed if the investigator deems them to be necessary to fully evaluate an AE. In the event that the investigator elects to order non-protocol-specified laboratory tests, the investigator must record the rationale for the tests and a determination of clinical significance of the result in the source documents. The investigator must keep the sponsor’s medically responsible person informed of vaccine-related AEs of medical importance.

Abnormal results and findings will be discussed as applicable with the participant, and the participant will be referred for follow-up with their healthcare provider if necessary.

3.6.3.3 Adverse Events

The collection periods for AEs are shown in Table 3-3.

Table 3-3 Collection Periods for Adverse Events

Type of Event	Collection Period
Unsolicited adverse events (non-serious)	First 14 days after each vaccination (spontaneous adverse events, if any) Diary review and interview at study visit 14 days after each vaccination.
Solicited adverse events	First 7 days after each vaccination (solicited adverse events recorded daily in diary card) Diary review and interview at study visit 14 days after each vaccination.
Adverse events of special interest	Entire post-vaccination study period (i.e., 421 days).
Serious adverse events including medically important adverse events	Entire post-vaccination study period (i.e., 421 days).

Solicited AEs are events the participant is specifically asked about. These AEs are commonly observed soon after the receipt of vaccination. For this study, solicited AEs to be collected include:

- Injection site reactions
Redness, swelling, tenderness/pain

- Systemic adverse events

Fever, Arthralgia, Myalgia, Fatigue, Headache, Rash, Chills, Nausea

Solicited injection site reactions will be considered causally related to the investigational product.

Adverse events of special interest represent a subset of AEs that include autoimmune diseases and other systemic disorders of interest that could potentially have an immune etiology. AEs of special interest are listed in Appendix A. The PI should use clinical and scientific judgment in deciding whether other AEs (i.e., events not listed in Appendix A) could have an autoimmune origin. The investigator will report AEs of special interest in the eCRF, hereby informing the sponsor's medically responsible persons.

All participants will be provided a diary card, a thermometer to record axillary temperature, a ruler to measure injection site redness and swelling, and instructions on how to use the diary for AE and CM recording, for the first 7 days after each vaccination.

In the period from 8 days after the vaccinations and until the diary card review at 14 days after each vaccination the participants are instructed to fill in the diary only in case they experience an AE or CM intake.

3.6.3.4 Site of Injection Examination

The injection sites will be examined immediately after the vaccinations, see section 3.6.3.1. After this, examinations for injection site reactions and loco-regional reactions such as axillary lymphadenopathy will be performed at the visits V4= Day 14 and V6= Day 70, see Table 3.1. The following will be assessed at these examinations:

- Redness, swelling, tenderness/pain and axillary lymphadenopathy

3.6.3.5 Concomitant Medications

The collection of information on CMs used by participants following vaccination will coincide with the collection period of AEs. In addition, information on all CMs associated with the treatment of AEs, SAEs and AEs of special interest, will be collected throughout the study.

CM includes prescription and non-prescription drugs or other treatments, and any vaccines other than the investigational product. The name of the medication, treatment start and stop dates (or 'ongoing'), and indication must be recorded on the CM page in the electronic case report form (eCRF). The indication recorded on the CM eCRF page must correspond to a medical term/diagnosis recorded on the AE eCRF page, or to a pre-existing condition noted in the participant's medical history, or be noted as prophylaxis.

3.6.4 Participant Follow-up and Contact

All participants who are assigned a randomization number and receive the first vaccination will be followed according to the protocol unless consent is withdrawn.

The participants will be instructed to contact a study team member to report new signs and symptoms or new or worsened AEs and will be referred for medical attention as applicable. For emergencies and other unscheduled visits to a medical facility other than the study site, medical records will, to the extent possible, be obtained by the investigator.

During each scheduled study visit or contact, the participants will be reminded to notify a study team member of the following:

- The occurrence of AEs and SAEs during the respective reporting periods.
- Receipt of any CMs during the applicable reporting period.
- Plans to move or if contact information changes.
- If participant has decided to withdraw from the study.
- Change in general health status including TB symptoms screen.
- Any other change in status that may affect the participant's participation (e.g., pregnancy, plan to participate in another investigational study).

Participant-level deviations from protocol procedures, evaluations, and/or visits must be documented. When possible, missed visits and procedures must be rescheduled and performed at the nearest possible time point to the original schedule. Deviations will be reported to the IRB/IEC and applicable national regulatory authorities per their guidelines.

3.6.5 Lost to Follow-up

If the study site's study team members are unable to establish contact with a participant who misses a scheduled study visit, the study site must make every possible effort to re-establish contact and document such efforts. If contact is re-established, then the participant will resume participation in the study. If contact with the participant cannot be re-established by the participant's calculated V8= Day 421 visit date, then a determination of "lost to follow-up" should be made on the date of the last contact.

4 INVESTIGATIONAL PRODUCT

4.1 Description of Investigational Product

The administered volume is 0.5 mL for all doses of investigational product. Please refer to the most recent version of the Vaccine Management Manual and IB, for further details regarding the investigational product.

H56:IC31

The H56:IC31 vaccine is manufactured, filled into vials and labelled at SSI according to GMP. The inner labels are study specific while the labels for the outer packaging (i.e. the cardboard boxes) are study and site specific. Both are produced at SSI. H56:IC31 will be supplied in single dose vials by SSI at a concentration of 5 µg/0.5 mL with IC31 at a concentration of 500 nmol KLK and 20 nmol ODN1a/0.5 mL.

Placebo:

A 0.9 % saline placebo will be purchased commercially and used as a comparator in the study. A label should be placed on the external carton stating the protocol number and that

the saline is for clinical use only.

4.2 Receipt, Storage and Accountability

Upon receipt of investigational product, the study vaccine manager must immediately inspect all vials for damage. Investigational product will be shipped with a continuous temperature-monitoring device. Any damage or discrepancies from the packing list must be documented and promptly discussed with the sponsor and the study monitor to determine the appropriate action.

H56:IC3 must be stored between +2°C and +8°C in a secured location with no access for unauthorized and blinded personnel. The normal saline placebo will be stored according to manufacturer's requirements in the study pharmacy.

Refer to the most recent version of the Vaccine Management Manual for detailed instructions regarding investigational product storage.

It is the site PI's responsibility that all unused and used vials are accounted for during the study and documented in the relevant study documents/logs. The study vaccine manager is delegated to maintain accurate investigational product accountability records. Instructions and forms to be completed and kept for accountability will be provided by the sponsor to the study vaccine manager. Upon completion of the study, all investigational product management records will be copied and the copies returned to the sponsor. The originals must be maintained at the study site with the rest of the study records. During the study an unblinded monitor will check that drug accountability is maintained.

4.3 Preparation

Refer to the most recent version of the Vaccine Management Manual for detailed instructions.

4.4 Disposal of Unused Investigational Product

After completion of the study the destruction of all used and unused vials is to be performed according to local regulatory and sponsor requirements. The destruction of investigational product may not be performed before the sponsor's acceptance has been given in written form. Any disposal of investigational product conducted at the clinical study site must be documented in the site study file.

5 SAFETY

5.1 Responsibilities for Ensuring the Safety of the Study Participants

The national regulatory authority, IRB/IEC, the study sponsor, the institution through which the research is performed and all members of the site PI's clinical team share the responsibility for ensuring that participants in this study are exposed to the least possible risk of adverse events that may result from participation in the study.

5.1.1 Principal Investigator

The site PI from each study site has a personal responsibility to closely monitor participants and an inherent authority to take whatever measures necessary to ensure the safety of the participants. The site PI has the authority to terminate, suspend or require changes to a clinical study for safety concerns and may delay an individual's investigational product administration. The site PI is responsible for determination of intensity, seriousness and causality with respect to the investigational product for each adverse event.

The site PI may delegate specific tasks to a designee who is a medically qualified team member (who must be a sub-investigator in the case of assessment of adverse events).

5.1.2 Study Sponsor

For this study SSI and IAVI are sharing sponsor responsibilities as co-sponsors. The sponsor has an institutional responsibility to ensure the safety of all participants in the study.

5.1.3 Medically Responsible Person

The medically responsible person in the study is a physician from the sponsor. The medically responsible person will review the safety of the product during the study and will assess the causality of the reported SAEs and provide the expectedness of related SAEs. The medically responsible person is like the site PI, blinded in this study.

Each co-sponsor has a medically responsible person who contributes to performing these tasks.

The site PI can, in case of an emergency, unblind a participant's treatment through a restricted access module in the eCRF (see Section 3.4.1).

5.1.4 Internal Data Review Committee and Independent Data Safety Monitoring Board

An internal data review committee, consisting of the coordinating PI, the site PIs and the medically responsible person from each of the co-sponsors, will convene during the study to review the blinded reported SAEs, AEs including AEs of special interest, injection site reactions and laboratory safety test results to identify any possible safety issues when:

- The first 150 participants across all sites have received their 1st vaccination and the 14 days safety follow-up data is available
- The first 150 participants across all sites have received their 2nd vaccination and the 14 days safety follow-up data is available

Randomization and vaccination will continue unless a stopping rule is triggered.

In case a stopping rule is triggered at any time by the site PIs and/or sponsor's medically responsible person, the study will be paused. Please see Section 6 for further details.

An independent DSMB will be established, consisting of a panel of independent experts, who will operate according to a DSMB charter. The DSMB will be convened if:

- A stopping rule is triggered
- The internal data review committee requests a DSMB meeting based on their review of the safety data

Based on the DSMB review, the DSMB will make recommendations to the sponsor regarding further conduct of the study and further administration of the investigational product.

The DSMB may require unblinding of any amount of safety information needed to conduct their assessment. All procedures associated with their review, including objectives, data handling, and elements to be included for review will be documented in the DSMB minutes.

The DSMB may recommend suspension or resumption of enrollment and investigational product administration after review of the safety data. However, the sponsor will make the final decision to suspend or resume study activities. The recommendations of the DSMB, along with the sponsor's decision, will be communicated to the site PIs, IRB/IEC, and the national regulatory authorities. The sponsor agrees to abide by any directives issued by the national regulatory authorities or the IRB/IEC.

5.1.5 Institutional Review Boards and Independent Ethics Committees

The IRB/IEC has institutional responsibility for the rights, safety, and welfare of participants in clinical studies. The IRB/IEC has the authority to terminate, suspend or require changes to a clinical study.

5.1.6 National Regulatory Authority

Each national regulatory authority receives all SUSARs and periodic safety reports summarizing the SAEs in the study and has the authority to terminate, suspend or require changes to the clinical study.

5.2 Definition of Adverse Event

Adverse event means any untoward medical occurrence associated with the use of a product in humans, whether or not considered product related, if deemed clinically significant by the investigator. An AE can be any unfavorable and unintended sign (e.g., an abnormal laboratory finding), symptom, or disease temporally associated with the use of a product, and does not imply any judgment about causality. An AE can arise with any use of the product (e.g., off-label use, use in combination with another product) and with any route of administration, formulation, or dose, including an overdose.

Medical conditions that exist prior to administration of the investigational product (pre-existing conditions) will be recorded in the eCRF on the participant's medical history page to establish baseline. Day-to-day fluctuations in pre-existing conditions that do not represent a clinically significant change in the participant's status will not necessarily be reported as AEs.

Any adverse change from the participant's baseline condition (determined from screening evaluations conducted to confirm study eligibility) that occurs following the administration of the investigational product will be considered an AE. This includes the occurrence of a new AE or the worsening of a baseline condition, whether or not considered related to the investigational product. Intermittent conditions such as headaches may be present on Study Day 0 but may represent an AE if the intensity or duration of the event is worse than usual following receipt of the investigational product. AEs include but are not limited to: adverse changes in the general condition of the participant, signs and symptoms noted by the participant, concomitant disease with onset or increased intensity after investigational product administration, and changes in laboratory and vital sign safety parameters considered clinically significant by the investigator occurring after investigational product administration.

AEs will be reported using a recognized medical term or diagnosis that accurately reflects the event. AE evaluations will be reviewed by the site PI or sub-investigator. AE information is to be completed by members of the study team designated by the site PI. The onset and resolution dates of the event and action taken in response to the event will be documented.

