2.1.2.1 Key Secondary Endpoints

- Solicited adverse events and all adverse events occurring the first 14 days after each of the 1st and 2nd vaccinations
- Serious adverse events including medically important events occurring after the 1st vaccination through the end of the study

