5.3 Assessing Intensity of an Adverse Event

The safety concepts of "intensity" and "seriousness" are distinct concepts (see Section 5.7). Intensity refers to a degree of clinical manifestation. "Seriousness" refers to defined outcomes of an AE. A severe AE is not always serious and a serious AE is not always severe.

For all AEs, the investigator is responsible for assessing the intensity of the event, the seriousness and the causal relationship of the event to the investigational product.

The **intensity** of all AEs, will be classified as one of the following grades:

1. **Mild**
2. **Moderate**
3. **Severe**

- "Mild" events are generally regarded as noticeable but have no impact on normal activities; they may or may not require over-the-counter treatment managed by the participant.
- "Moderate" events generally have some impact on an individual's normal activities and may require general symptomatic medical intervention by a healthcare professional or by the participant.
- "Severe" adverse events may be incapacitating, leading to suspension of normal daily activities, and would generally require more immediate medical evaluation and intervention by a healthcare professional.

A change in intensity of an AE will not be recorded as a new AE. Only the highest intensity level that occurs during the entire period of the AE will be recorded in the eCRF with the onset and resolution dates encompassing the entire duration of the event.

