5.13 Participant Diary

Day 0-7 after each study vaccination:

All participants will be asked to fill in a diary daily for 7 days after each vaccination. In the diary the participants are asked to measure and report on the day of vaccination and the following 7 days details of the following AEs:

- Solicited:
 - Injection site reactions (Redness, Swelling, Tenderness/Pain)
 - Systemic AEs (Fever, Arthralgia, Myalgia, Fatigue, Headache, Rash, Chills, Nausea)
- Any other symptoms

Solicited injection site reactions will be considered causally related to the investigational product.

All participants will receive and be instructed in completing the diary. A ruler (for measurement of injection site reactions) and a thermometer (for axillary use) to be used

during the specified post-vaccination diary period after each study vaccination will be provided. The diary is a tool to aid the investigator to engage in a conversation with the participant about any AEs and/or CM intake that may have occurred between visits.

If a diary is lost, the investigator will discuss the occurrence of any AEs and/or CM with the participant and document the discussion. The diary will be considered source documentation and information assessed to be an AE by the investigator will be recorded in the eCRF. Source should document the clinical significance assessment.

Any change to an observation or event recorded by the participant in the diary based on the investigator's evaluation of the event, must be explained by notation in source documentation by the investigator.

Day 8-14 after each study vaccination:

From day 8-14 after each study vaccination the participants are instructed to fill in the diary only in case they experience an adverse event(s) (or concomitant medication intake). The participant will on day 14 after each vaccination be interviewed by the investigator, if any signs or symptoms have been observed by the participant.

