7.4.7 Injection Site Reactions

The number (percentage) of participants recording injection site reactions (redness, swelling and tenderness/pain) and axillary lymphadenopathy will be summarized by treatment group and post-vaccination time point. In addition, measurements (recorded in mm) of redness and swelling will be summarized as continuous parameters by treatment group.

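### Protocol 5.2 and 5.13 allow clinical-significance judgement to decide which solicited diary reactions reach a key secondary safety endpoint, while other protocol text points to recording them all

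*Protocol*

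**What the plan says.** **Definition.** Protocol 5.2 opens by making an untoward occurrence an AE "whether or not considered product related, if deemed clinically significant by the investigator". Its third paragraph sets no such condition: any adverse change from baseline "that occurs following the administration of the investigational product will be considered an AE". The examples there include symptoms the participant notices. In that list, clinical significance qualifies only laboratory and vital-sign changes.

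**Diary.** Under Protocol 5.13, participants record three injection site reactions and eight systemic symptoms from the day of vaccination through Day 7. Then: "The diary will be considered source documentation and information assessed to be an AE by the investigator will be recorded in the eCRF". The paragraph ends: "Source should document the clinical significance assessment". No sentence exempts solicited items. The one automatic rule for solicited injection site reactions fixes their causality, not whether they are entered.

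**Contrary text.** Protocol 2.2 says that solicited AEs, including injection site reactions, are assessed and recorded at V4 and V6, with no significance condition.

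**Endpoint.** The first key secondary endpoint in Protocol 2.1.2.1 is "Solicited adverse events and all adverse events occurring the first 14 days after each of the 1st and 2nd vaccinations".

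**Analysis.** SAP 7.2.1 defines solicited AEs as events of given types within 7 days of a vaccination, and identifies fever by its coded preferred term. The solicited listings (16.2.7.2 and 16.2.7.3) carry an AE number. A footnote to Listing 16.2.7.10 takes injection site reactions from events so marked in the eCRF. Table 14.3.2.3 counts reactions that have a recorded size.

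**The concern.** Solicited reactogenicity is normally useful because every participant is asked the same questions on the same days and the answers are tabulated as given. A judgement placed between the diary and the database removes part of that standardisation. Neither document gives a size, temperature or symptom threshold for clinical significance of a solicited item, so the judgement would be local to each of six sites in two countries.

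Mild reactions are the most exposed. Protocol 5.3 says mild "events are generally regarded as noticeable but have no impact on normal activities", and Protocol 1.4 describes the vaccine's common reactions as mild to moderate. At stake are the absolute reactogenicity rates that the report will give for this vaccine, and the comparability of those rates across sites. The internal data review committee's two looks at the first 150 participants also use reported events, so they would inherit any omission.

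**Working it through.** No figure in the plan depends on this point, so there is none to reproduce. The check is to follow one solicited symptom from diary to table, then illustrate what a filter would do.

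**Tracing a mild injection site pain, noted on Day 2**

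1. The participant writes it in the diary (5.13). It is a listed solicited item.
2. The investigator decides whether it is an AE. Under the first sentence of 5.2 it is one only if deemed clinically significant. Under the third paragraph it is one without that test.
3. If assessed to be an AE, it enters the eCRF (5.13). If not, 5.13 does not require entry, and the significance assessment stays in source.
4. The SAP's solicited tables, plots and listings start from eCRF events. No planned output uses diary responses that did not become events, so the analysis cannot recover an omission at step 3.

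A site that enters the pain and a site that does not can each point to protocol text. The documents settle neither which rule applies nor how often the choice arises.

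**Illustration (assumed inputs)**

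The documents give no reaction rates for this trial. Let p be the true share of participants with at least one solicited reaction, and q the share of those participants who have at least one reaction entered. Defining q per participant matters: someone who loses a mild event but keeps a moderate one is still counted.

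Recorded rate = p × q. With the same q in both arms, the risk difference is multiplied by q and the risk ratio is unchanged. Assume p = 40% on vaccine and 20% on placebo:

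| q | Vaccine | Placebo | Difference | Ratio |
|---|---|---|---|---|
| 1 | 40% | 20% | 20 points | 2.0 |
| 0.75 | 30% | 15% | 15 points | 2.0 |
| 0.5 | 20% | 10% | 10 points | 2.0 |
| 0.25 | 10% | 5% | 5 points | 2.0 |

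Across sites: with the same true rate of 40%, a site with q = 1 reports 40% and a site with q = 0.5 reports 20%.

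The ratio moves only if q differs by arm. With q = 0.5 on vaccine and 0.75 on placebo it is (0.40 × 0.5)/(0.20 × 0.75) = 0.20/0.15 = 1.33. With the two values exchanged it is 0.30/0.10 = 3.0.

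**The case against.** The best defence is that the protocol, read as a whole, intends all solicited items to be recorded. Section 2.2 says so. Section 3.6.3.3 lists them as AEs to be collected, 5.13 itself calls the diary items AEs, and Table 3-1 gives them a row separate from other non-serious AEs. Section 5.13 also makes the diary a source document and requires a source note whenever the investigator's evaluation changes an entry. This is a fair account of likely intent, but it leaves two rules standing. The source note keeps a trail at the site, not in the analysed data.

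Three stronger readings are tempting, and the documents do not support them.

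- **That mild reactions would be left out.** Nothing equates mild with not clinically significant. Section 5.3 grades all AEs, including mild ones that may need over-the-counter treatment. The SAP shells have rows for mild events, and SAP 7.2.1 plots solicited reactions by maximum severity. Mild events are expected in the data; what is missing is assurance that all of them are there.
- **That Protocol 7.4.7 promises diary counts.** It speaks of "The number (percentage) of participants recording injection site reactions", but the same sentence covers axillary lymphadenopathy, which is not a diary item and is found by examination at V4 and V6 (3.6.3.4).
- **That the arm comparison is biased.** Unblinded site staff may not evaluate AEs (3.4), and causality is judged without knowledge of allocation (5.4). Different filtering by arm would need a further mechanism, such as reactions suggesting the allocation, and the documents give no evidence of one.

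It also stands that the diary form, the eCRF and the site instructions are not among the documents. They may already require full entry.

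**Conclusion.** The point holds as a contradiction with a practical consequence. Section 5.2 gives two definitions of an AE, 5.13 applies the stricter one to the diary, 2.2 points the other way, and the SAP has no route back to the diary. Some solicited reactions could therefore be missing from a key secondary endpoint, to a degree that depends on site practice.

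The size is unknown. The text shows that a filter is permitted, not that it operated or how many reactions it removed; the table above shows direction only. The expectation of lower absolute rates and a smaller risk difference with an unchanged ratio assumes a similar q in both arms. Blinding makes that reasonable, but it also needs a broadly similar mix of intensities in the two arms, on which the documents give no data. SAP 6.6 plans no formal testing outside the efficacy endpoints, so the consequence is for the description of reactogenicity, not for a test result. The primary efficacy analysis is unaffected. The change is worth making because it is cheap and concerns a safety endpoint.

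**What to change.** - **Protocol 5.2:** limit the clinical-significance condition to laboratory, vital-sign and examination findings, so that the opening sentence agrees with the third paragraph.
- **Protocol 5.13:** require every solicited diary item for Days 0-7 (presence, worst intensity, size of redness or swelling, highest axillary temperature) to be entered in the eCRF whatever its clinical significance, with any investigator correction documented.
- **SAP 7.2:** derive solicited reaction rates, sizes and maximum temperatures from those entries.
- **If data were already collected under the current wording:** state in the SAP and the report that entry was subject to this judgement, and add a diary-based solicited summary where the source diaries allow. Protocol 8 keeps source documents for at least 15 years.

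The cost is protocol and eCRF wording, more routine data entry from a diary already collected, and probably a less favourable reactogenicity profile. No visit or test is added.
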